### ***Sensitivity Analysis***

#### **Definition of treatment and control group**

We adopt a conservative approach in our primary analysis and define any child as part of the control group whose local authority had not implemented Family Safeguarding at the start date of the first referral within the trial period. This will most likely underestimate the treatment effect, since children in the control group might have been in contact with Family Safeguarding at a later stage of the referral.

To analyse the magnitude of the treatment effect further, we run additional regressions using different treatment and control group definitions. We will look at different treatment definitions including:

- Children whose spent at least half their time on any open referrals in the trial period when the local authority had implemented Family Safeguarding, i.e. if a child had 64 days of open referrals during the trial period, and had at least 32 of those days after the local authority had implemented Family Safeguarding, they would be coded 1, otherwise coded 0.
- Children who spent at least 4 weeks across any open referrals during the trial period under Family Safeguarding coded as 1, otherwise coded 0.

#### **Non-parametric permutation test**

To check the robustness of our results, we will seek to conduct a non-parametric permutation test for testing the null hypothesis of no treatment effect. The permutation test can provide an alternative to the GLMM models used in our primary analysis, as it remains valid in small samples and in the presence of correlation across different clusters regardless of the underlying data distribution. It is also robust to mis-specification of the models used to construct the test statistics. The permutation test generally works well with a small number of clusters but in the current research design of five clusters only, the evidence is more scarce. Hence, we include this test only as a sensitivity analysis to support the main analysis.

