## Randomisation

The level of randomisation is at the local authority level. Due to the stepped-wedge evaluation design, we randomise the order in which local authorities implement the programme, in six month intervals, rather than which local authority implements the model. The randomisation will be stratified by the level of readiness of participating local authorities. Each local authority will be classified as either 'high readiness', for those that are in a position to implement the model sooner, and second for the 'low readiness' authorities, for those that will need longer to implement the model. Two local authorities were identified as 'high readiness', and three as 'low readiness'.

The two local authorities classified as 'high readiness' will be randomly assigned to implement the model either first or second. Those classified as 'low readiness' will also have the order randomised in which they will implement the model, following the high readiness local authorities (so they will be the third, fourth, and fifth local authorities to implement the model).

The division of local authorities into more or less ready tranches is meant to avoid implementation failure caused by choosing local authorities to receive the intervention that are not yet ready. The assessment of readiness was conducted by the developing local authority Hertfordshire in collaboration with the Department for Education (DfE). Our strata are thus very small strata (2-3), which normally would be avoided but was necessary in order to be able to implement the evaluation. However it is a notable constraint on our randomisation, that will affect the robustness of our results. This will be reflected in the evidence strength rating awarded to the final study.

To avoid potential contamination, local authorities whose implementation start date has not yet passed have to commit to business-as-usual practices to enable a treatment and control group comparison in each time period. However, they will be given permission to begin preparation to implement, so long as it would not influence the current practice in the local authority.

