## Analysis plan

### Primary Analysis

We will assess the impact of Family Safeguarding Model on the primary outcomes of interest  $Y_{iat}$  in the following GLMM regression framework:

$$\text{logit}(Y_{iat}) = \beta_0 + \alpha_{0a} + \beta_1 FS_{iat} + \sum_{i=1}^5 \beta_{i+1} I(t = i) + \gamma X_{iat} + \rho Z_{at} + \varepsilon_{iat}$$

Where

- $Y_{iat}$  is a binary indicator that equals 1 if the child entered care within 24 months of their first referral in the trial period, and 0 otherwise.
- $\alpha_{0a}$  is a (normally distributed) random intercept at the level of the cluster. This random effect estimates the stochastic variation of individual clusters around the conditional mean of the clusters.
- $\beta_2 - \beta_6$  are a series of indicator variables adjusting for time trends by introducing dummy variables for each time after the baseline period  $t = 0$ .
- $FS_{iat}$  is a binary indicator that is equal to 1 if the child had its first referral during the trial period after the local authority implemented Family Safeguarding (and 0 if before).
- $X_{iat}$  is a vector of individual and household level characteristics that may also influence the outcome, such as age of the child, gender, and household SES.
- $Z_{at}$  is a vector of time-varying local authority characteristics, such as the number of children per local authority or the turnover rate of staff.
- $\varepsilon_{iat}$  are the errors at time  $t$  for individual  $i$ .

The GLMM is an extension of the GLM for analysing correlated data. The unit of analysis is at the individual level to optimise the power to detect an effect within the constraints of the project. We use a logistic regression within the GLMM framework to account for the binary nature of our outcome variable and because the baseline rate is low.

We will judge the statistical significance of the treatment effects applying a significance level of 5%. Due to the small number of clusters, we cannot cluster or bootstrap standard errors via any conventional method. However, we will consider whether or not applying a wild bootstrap with a correction for the small number of clusters is appropriate in this instance. Our sensitivity analysis will consider different evaluation approaches that are discussed in detail below.

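### The stratified randomisation allows only 12 implementation orders, so the planned permutation test cannot give p below 0.083 and cannot check robustness at the 5% level

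*Protocol*

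**What the plan says.** Under Randomisation, the protocol states that "we randomise the order in which local authorities implement the programme, in six month intervals" and that "The randomisation will be stratified by the level of readiness of participating local authorities". The stratum sizes follow: "Two local authorities were identified as 'high readiness', and three as 'low readiness". The high-readiness pair "will be randomly assigned to implement the model either first or second". The other three are randomised among the remaining places, "so they will be the third, fourth, and fifth local authorities to implement the model".

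Under Primary Analysis, the protocol says "We will judge the statistical significance of the treatment effects applying a significance level of 5" per cent. The table under Sample size / MDES calculations gives alpha 0.05, two-sided. No other significance level appears.

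Under Sensitivity Analysis, the subsection Non-parametric permutation test plans a test of no treatment effect to check the robustness of the main results, "as it remains valid in small samples and in the presence of correlation across different clusters regardless of the underlying data distribution". It adds one caution, that "in the current research design of five clusters only, the evidence is more scarce", and for that reason keeps the test as a sensitivity analysis. It does not give the set of orders to be permuted, their number or the smallest p-value they allow.

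**The concern.** A randomisation-based permutation test compares the observed statistic with its values under every order that the randomisation could have produced. If there are few such orders, the p-value has a floor that no sample size or effect size can lower. Here the floor is above the protocol's only significance level.

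The check matters because of what surrounds it. The Primary Analysis section accepts that, with so few clusters, standard errors cannot be clustered or bootstrapped by the usual methods, and it promises only to consider a wild bootstrap. The permutation test is the one listed check on the model-based p-value that draws its validity from the randomisation itself. If it is read against 5%, its result is known before any data arrive, and a real effect could be reported as not confirmed. If the reference set is left open, the choice between 12 and 120 orders decides whether significance is possible at all, and that choice could be made after the results are seen.

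**Working it through.** **Inputs**
- Five authorities, one starting at each six-month step (Randomisation).
- Two high-readiness authorities in places 1 and 2; three low-readiness authorities in places 3 to 5 (Randomisation).
- Significance level 5% (Primary Analysis); alpha 0.05, two-sided (MDES table).
- Baseline 0.06, 1,700 children per authority and period, ICC 0.00722, five steps (MDES table and Appendix B).

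**Step 1: reproduce the plan's own figure.** The protocol gives no permutation count, so the MDES serves to confirm the layout. It uses the standard stepped-wedge variance with I = 5 clusters and T = 6 periods:

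Var = I s²(s² + T τ²) / [(IU − W)s² + (U² + ITU − TW − IV)τ²]

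- Design sums: U = 15, W = 55, V = 55. So IU − W = 75 − 55 = 20, and U² + ITU − TW − IV = 225 + 450 − 330 − 275 = 70.
- Total variance: 0.06 x 0.94 = 0.0564.
- τ² = 0.0564 x 0.00722 = 0.000407; s² = 0.0564 x (1 − 0.00722) / 1,700 = 0.0000329.
- SE = 0.00374. MDES = (1.960 + 0.842) x 0.00374 = 0.01048.

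This matches the stated 0.0105. The total of 5 x 6 x 1,700 = 51,000 also matches.

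**Step 2: count the possible orders.**
- High readiness: 2! = 2. Low readiness: 3! = 6.
- Possible orders: 2 x 6 = 12. Enumeration gives 12 distinct schedules.

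**Step 3: find the floor of the p-value.**
- Two-sided p by absolute statistic: 1/12 = 0.083.
- One-tailed p doubled: 2/12 = 0.167.
- Both exceed 0.05.

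**Step 4: ignore the strata.**
- 5! = 120 orders; floor 1/120 = 0.008.
- Orders that could not have occurred: 120 − 12 = 108, or 90%.

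**Step 5: simulate.** There were 1,000 runs per effect size, using authority-by-period means at the protocol's baseline, ICC and cell size. Assumptions: normal errors, period effects with SD 0.005 and authority effects drawn from one common distribution. The statistic was the absolute two-way fixed-effects estimate.

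| True effect | 12 orders, p ≤ 0.05 | 12 orders, p ≤ 0.10 | 120 orders, p ≤ 0.05 |
|---|---|---|---|
| 0 | 0% | 8.3% | 4.8% |
| 0.0105 | 0% | 61.3% | 71.6% |
| 0.02 | 0% | 96.9% | 99.9% |
| 0.05 | 0% | 100% | 100% |

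The smallest p seen with 12 orders was 0.083, so ties in the absolute statistic do not force the floor higher. Attainable p-values are multiples of 1/12, so p ≤ 0.10 means that the observed estimate ranks first of 12. The 120-order column treats authorities as exchangeable by construction, so it cannot show what happens if readiness groups differ.

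**The case against.** The case against has four parts.

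**The praise of the test is correct.** A reader might infer that the protocol's claim of validity is false. It is not. Validity means control of the false-positive rate, and the 12-order test has that. The fault is resolution, not validity. This stands.

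**The permutation subsection does not state 5%.** A reader might infer that the plan commits the test to that level. The level is given under Primary Analysis and is not repeated. This stands as a matter of text. But 5% is the only level in the protocol, and a check on whether the main result is robust will naturally be read against it unless the plan says otherwise.

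**Permuting 120 orders need not inflate error.** A reader might infer that it would yield a false confirmation. The documents do not support that. Such a test can hold its level if authorities are exchangeable under the null, and it did so in the simulation (4.8%), where exchangeability was built in. What it lacks is a basis in the randomisation. The assumption is not trivial here, since readiness decided who went early. Nor does the protocol say that all 120 orders will be used.

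**The limits are partly disclosed, and details belong in a statistical analysis plan.** The permutation subsection hedges on five clusters, and the Randomisation section admits that the very small strata weaken the results. Neither mentions the floor, and presenting the matter as scarce evidence makes a fixed, knowable limit look like an open question. A statistical analysis plan could name the reference set, but it could not bring a 12-order test to 5%.

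**Conclusion.** The point holds, with moderate severity. A permutation test based on this randomisation has a smallest p of 0.083 (0.167 if a one-tailed p is doubled) and zero power at 5%. This follows from the stratum sizes alone and needs no assumption about the data. The 61% chance of ranking first of 12 at the stated MDES does depend on the simulation assumptions, and its Monte Carlo standard error is about 1.5 points (√(0.613 x 0.387 / 1,000) = 0.015). It shows that the test still carries information when read as a rank.

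A reader might go further and conclude that the main result is compromised. The documents do not support that: the test is labelled a sensitivity analysis and has no decision role, and the primary model, its 5% criterion, the MDES and the sample size are all unaffected. What is affected is how the check may be read.

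**What to change.** Amend the permutation test subsection before outcome data are obtained. The Sample size section already foresees a protocol update in that window.

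- Name the 12 stratum-respecting orders as the reference set.
- Define the two-sided p as the share of the 12 orders whose absolute statistic is at least as large as the observed one.
- State that the smallest attainable p is 1/12 = 0.083.
- Report the observed rank among the 12 and the exact p as descriptive evidence, not against 5%.
- State that a p above 0.05 from this test is not to be read as failure to confirm the main result.
- State that any claim at 5% rests on the model and not on the randomisation.

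A formal criterion of 1/12 with a matching 91.7% (11/12) interval would be a preference, not a needed correction, and the criterion could never be met if a one-tailed p were doubled.

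The cost is wording only, with no new data and no change to the primary analysis. The downside is that the report must admit that randomisation-based evidence in this trial cannot reach 5%.

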#### **Differential time effects**

We do not consider time effects such as embedding periods in our primary analysis. It may be that Family Safeguarding needs some time to be fully embedded and functional. In that case the treatment will show differential time effects. In this sensitivity analysis, we thus

---

 Wang, R. & De Gruttola, V. (2017): The use of permutation tests for the analysis of parallel and stepped-wedge cluster-randomized trials

include differential treatment effects depending on the time passed since Family Safeguarding has been implemented in the local authority. The regression specification is:

$$\text{logit}(Y_{iat}) = \beta_0 + \alpha_{0a} + \beta_1 FS_{iat} + \sum_{m=0}^M (FS_{iat} \cdot T_{t+m}) \delta_{m+1} + \sum_{i=1}^5 \beta_{i+1} I(t=i) + \gamma X_{iat} + \rho Z_{at} + \varepsilon_{iat}$$

where  $T_{t+m}$  is a binary indicator that equals one if the observation is from a local authority that has been implementing Family Safeguarding for  $m$  periods, and otherwise 0. The coefficients on the interaction effect will shed light on whether authorities experience increasing treatment effects the longer they run Family Safeguarding.

We recognise that the estimation of differential time effects will likely be underpowered due to splitting the treatment effect into separate, time-dependent effects. Nevertheless, we consider this analysis as potentially providing a richer picture of the effects of Family Safeguarding.

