## Context

The IPE and RCT parts of the evaluation will be undertaken in the local authorities funded by the Department for Education to introduce Family Safeguarding as part of the Strengthening Families, Protecting Children programme, with the exception of the Trailblazer who is participating in a separate pilot evaluation. These local authorities are due to launch Family Safeguarding at six-month intervals beginning in April 2020. In the order they will be rolled out, these local authorities are Walsall, Lancashire, Telford & Wrekin, Wandsworth and Swindon.

All authorities had a judgement of ‘requires improvement to be good’ at the point at which they applied for the programme. However, at the point of rollout to the first local authority, Children’s Services in three of these authorities (Walsall, Lancashire and Wandsworth) have an Ofsted judgement of ‘requires improvement to be good’, while Swindon received a

judgement of 'good' in July 2019 and Telford & Wrekin received a judgement of 'outstanding' in January 2020. These authorities were selected by the Department for Education to participate in the programme due to having high rates of children looked after compared to their local authority statistical neighbour median over the last 3 years, and/or rising rates of children looked after in each of the last 3 years.

York Consulting is currently conducting a process evaluation of Family Safeguarding in four additional local authorities, namely Peterborough, Luton, Bracknell Forest and West Berkshire.

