For the purposes of this RCT, we will only consider children who have been in touch with children's social care between six-months before the first local authority's implementation date, and six-months after the last local authority's implementation date. We define the implementation date as the date the Family Safeguarding model is considered 'Operationally Live' in the local authority. The Operationally Live date has been set in advance by the Department for Education. When analysing the data, we may change the date we consider the intervention to have gone Operationally Live, if it becomes apparent that there have been significant changes in terms of the timings of the models core activities. This will only be done with the agreement with the Department for Education and consultation with the model developer. Any such changes will be detailed in the report. Specifically, the core activities are as detailed below.

[figure not shown]
By the Operationally Live date:

- Training in Motivational Interviewing and workshops by the model developers should have been delivered to all staff in family safeguarding teams.
- Specialist adult workers should be recruited and in post.

From the Operationally Live date:

- Staff should be using Motivational Interviewing and the parenting assessment and intervention programme with families,
- Staff should be recording case notes using the electronic workbook
- Group case supervision should begin taking place at regular intervals for cases with adult specialist worker involvement.

The diagram below illustrates the randomisation and intended timings of the implementation of Family Safeguarding across the local authorities. The trial period, as indicated in the diagram, takes place from 6 months prior to when the first local authority implements the model (or goes Operationally Live), and continues until 6 months after the final local authority implements the model.

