### ***Sample size and cluster size***

The sample size was derived from the estimated baseline population for our primary outcome, which is the number of children who have been referred in a six month period. We take the average across local authorities that form part of our sample to calculate the average cluster size. The sample size is derived from the average cluster size times the number of local authorities in the trial and the six periods of the stepped-wedge implementation.

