### Exploratory Analysis

#### High and low readiness of local authorities

Since the randomisation of the implementation date was stratified by the readiness of local authorities to implement Family Safeguarding, we explore a potential difference in effects of the implementation of Family Safeguarding between high and low readiness authorities.

$$\text{logit}(Y_{iat}) = \beta_0 + \alpha_{0a} + \beta_1 FS_{iat} + \beta_2 HR_a + \beta_3 HR_a * FS_{iat} + \sum_{i=1}^5 \beta_{i+3} I(t=i) + \gamma X_{iat} + \rho Z_{at} + \varepsilon_{iat}$$

Where:

- $HR_a$  is an indicator that is equal to 1 if the authority belongs to the high readiness group that first implements the programme, and 0 if they belong to the 'less ready' group.
- $HR_a * FS_{iat}$  is an interaction term that will allow for differential effects of the model on the local authorities in the high readiness tranche versus the low readiness tranche.  $\beta_3$  will be zero if the intervention affects the likelihood of a child entering care equally in both groups of local authorities.

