## Appendix B: Power calculations Stata code

```
steppedwedge, binomial detectabledifference complete(1) vartotal(0) p1(0.06) m(1700) k(1)  
rho(0.00722) alpha(0.05) beta(0.8) steps(5)
```

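### The time-since-go-live model shares one effect profile across all five authorities, so a difference in effect between authorities that is constant over time would appear as the effect growing or fading

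*Protocol*

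**What the plan says.** Under Differential time effects, the Protocol adds to the primary model indicators for the number of periods, m, that an authority has been running Family Safeguarding. The coefficients on these indicators are common to all authorities. The model has a random authority intercept, but neither a readiness-by-treatment term nor a treatment effect that varies by authority. The intended reading is explicit: "The coefficients on the interaction effect will shed light on whether authorities experience increasing treatment effects the longer they run Family Safeguarding". The only limitation stated is low power.

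Under Randomisation, order is randomised only within readiness groups. "The two local authorities classified as 'high readiness' will be randomly assigned to implement the model either first or second"; the low-readiness authorities come next, "following the high readiness local authorities (so they will be the third, fourth, and fifth local authorities to implement the model". The trial period "continues until 6 months after the final local authority implements the model".

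Under High and low readiness of local authorities, a separate exploratory model is planned in which "we explore a potential difference in effects of the implementation of Family Safeguarding between high and low readiness authorities". It contains no exposure-time terms. Nothing in the Protocol connects the two analyses.

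**The concern.** Whether authorities improve the longer they run the model is a question about change within an authority. The set of authorities that contributes to each coefficient shrinks as m grows, and it shrinks in an order fixed by readiness. Comparing late with early coefficients therefore partly compares the early adopters with everyone else.

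If the early, readier authorities simply have a larger effect from the first day, the model would suggest that the effect builds up. If they have a smaller one, it would suggest that the effect wears off. This is the only outcome regression in the plan that addresses embedding, so a funder could take from it that results improve or decay with time when neither happens in any authority.

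**Working it through.** **Inputs.** Five authorities, one per step, ICC 0.00722 (Protocol, Appendix B: "rho(0.00722) alpha(0.05) beta(0.8) steps(5"); "the six periods of the stepped-wedge implementation" (Sample size and cluster size); baseline 0.06, 1,700 children per authority per period and a minimum detectable effect of 0.0105 (Sample size / MDES calculations). Roll-out order is from Context: "In the order they will be rolled out, these local authorities are Walsall, Lancashire, Telford & Wrekin, Wandsworth and Swindon". The size of any difference in effect between authorities is not in the documents. It is assumed here, with a range of 0.5 to 1.05 pp between readiness groups; the upper end equals the plan's own detectable effect.

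**Step 1: reproduce the plan's figure.** Total variance = 0.06 × 0.94 = 0.0564. Between-authority variance = 0.00722 × 0.0564 = 0.000407. Cell-mean variance = 0.99278 × 0.0564 / 1,700 = 0.0000329. Generalised least squares (GLS) on the 5 × 6 = 30 authority-period cells, with period effects and one treatment effect, gives SE 0.00374. The detectable effect is (1.960 + 0.842) × 0.00374 = 0.01048, which matches the stated 0.0105.

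**Step 2: who contributes at each m.** The first to fifth authorities have 5, 4, 3, 2 and 1 treated periods.

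| m | Authorities by roll-out position | Readiness |
|---|---|---|
| 0 | 1–5 | both groups |
| 1 | 1–4 | both groups |
| 2 | 1–3 | two high, one low |
| 3 | 1–2 | high only |
| 4 | 1 | high only |

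The single m=4 cell falls in the last period, when every authority is already treated.

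**Step 3: what the shared-profile model returns when no effect changes over time.** The same GLS was fitted to noise-free data. As printed, the treatment term plus an indicator for every m from 0 is collinear (12 columns, rank 11), so the identified form with one effect per m was used (11 columns, rank 11).

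| True constant effects (pp) | m=0 | m=1 | m=2 | m=3 | m=4 |
|---|---|---|---|---|---|
| −1.05 in all five | −1.05 | −1.05 | −1.05 | −1.05 | −1.05 |
| −1.05 high, 0 low readiness | −0.549 | −0.715 | −0.975 | −1.317 | −1.505 |
| 0 high, −1.05 low readiness | −0.501 | −0.335 | −0.075 | +0.267 | +0.455 |

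The m=4 minus m=0 contrast weights the five authorities' effects by 0.613, 0.298, −0.022, −0.353 and −0.536. The two high-readiness weights sum to 0.911, so 0.911 of any readiness gap becomes false change:
- gap 0.5 pp: 0.911 × 0.5 = 0.46 pp
- gap 1.05 pp: 0.911 × 1.05 = 0.96 pp

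Fixed authority intercepts give nearly the same profile in the second scenario (−0.543 to −1.488). On the logit scale, a log odds ratio of −0.4 in the first two authorities and 0 in the rest gives −0.20 at m=0, running to −0.57 at m=4.

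**Step 4: set this against the noise.** The SE of m=4 minus m=0 is 0.90 pp. At a gap of 1.05 pp the ratio is 0.96 / 0.90 ≈ 1.06, so a two-sided 5% test rejects about 19% of the time. At 0.5 pp the ratio is 0.46 / 0.90 ≈ 0.51, and rejection is about 8%.

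**Step 5: test the repairs.** Both keep common increments for m≥1 relative to m=0.
- *Readiness-specific main effect* (rank 12 of 12). The false increments vanish if effects are equal within each readiness group, and otherwise do not. With a constant −1.05 pp in the third authority only, the increments for m=1 to 4 are −0.17, −0.42, −0.54 and −0.73 pp. With it in the fifth only, they run from +0.23 to +0.60 pp.
- *Authority-specific main effect* (rank 15 of 15). The false increments are exactly zero for any set of constant authority effects. The SE of m=4 minus m=0 becomes 1.35 pp.

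**The case against.** The plan is already modest here. This is a sensitivity analysis, described as probably underpowered, and the Randomisation section concedes that the readiness constraint weakens robustness. The readiness interaction will be reported too, so an attentive reader could put the two together. The Implementation and Process Evaluation (IPE) also follows delivery in each authority at 3, 12 and 24 months after its own go-live, and results are to be read alongside it. All of that stands, and it limits the importance of the point. It does not remove it: low power is imprecision around the right quantity, whereas this is bias that more data would not reduce. The readiness model has no exposure-time terms and so cannot correct the exposure profile.

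The documents do not support four stronger readings that a reader might infer:
- *That the model will show a clear false trend.* This requires effects to differ between authorities. The Protocol raises that as a possibility, neither expects it nor gives its size, and even a gap equal to the full detectable effect would usually not reach significance.
- *That this is the plan's only check on embedding.* It is the only outcome regression on it; the IPE tracks delivery over time separately.
- *That all later coefficients come from high-readiness authorities.* This is exact for m=3 and m=4; m=2 includes one low-readiness authority.
- *That growth and authority differences cannot be separated.* They can, at a cost in precision, as the full-rank model in Step 5 shows.

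**Conclusion.** The point holds conditionally. The printed model does not support the within-authority reading given to it, because readiness and length of exposure are tied by design and the model allows no difference in effect between authorities. Under an assumed constant gap of 0.5 to 1.05 pp between readiness groups, the false m=4 minus m=0 change is about 0.46 to 0.96 pp against an SE of 0.90 pp: biased, but often not significant. If effects are the same in all authorities, there is no bias. The figures rest on the plan's own inputs, a linear model on cell means and equal cell sizes. The primary estimate is not affected. The change is worth making before outcome data arrive, since it concerns one sensitivity model and the conclusion attached to it.

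**What to change.** Under Differential time effects, keep the printed model (dropping one redundant term) and add a second version beside it. This gives each authority its own Family Safeguarding main effect and has common increments for m≥1 relative to m=0. Base any statement that effects grow or fade on those increments. Do not settle for a readiness-specific main effect, for the reason shown in Step 5. State in the report that m=3 rests on two authorities and m=4 on one, and draw no conclusion about embedding from those two alone.

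The cost is a few more coefficients and no new data. The price is precision: the SE of m=4 minus m=0 rises from 0.90 to 1.35 pp, so the result will be imprecise and should be reported as such. One limit remains: the increments are still assumed common to all authorities, so growth that itself differs between authorities would not be separated.
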